[figure not shown]

## 1. General information of AGUEDA project

### 1.1 Background and rationale

Cognitive decline associated with dementia, particularly in Alzheimer's disease (AD) (1), initiates over two decades before clinical symptoms, with pathological accumulation of beta-amyloid in the brain as an early marker (2,3). Executive function and memory are the first cognitive domains affected (4). While memory decline is typical of AD, executive dysfunction may precede it (5) and predict further cognitive decline, mild cognitive impairment (MCI), and AD, making it a potential target for lifestyle interventions (6,7).

Dementia is not inherent to aging, and exercise stands out as a non-pharmacological preventive and efficient treatment for age-related cognitive decline (8). Systematic reviews have highlighted the benefits of exercise interventions in older adults, impacting executive function, memory, language, and general cognition (9–12). Although aerobic exercise has been extensively studied (13,14), resistance exercise, despite being included in physical activity guidelines, has received less attention (15,16). Recent reviews suggest significant cognitive benefits from resistance exercise (12,17,18), even at low doses (18). However, variations in study parameters make it challenging to determine the specific dose and type of resistance exercise needed for cognitive improvement (19). Therefore, well-designed randomized controlled trials (RCTs) are essential to clarify the effects of resistance exercise on cognition in older adults.

Potential mechanisms underlying exercise's cognitive benefits span molecular, brain structural/functional, and behavioral levels. Most evidence is derived from aerobic exercise studies, but resistance exercise may involve distinct pathways. Animal studies suggest inflammatory and metabolic changes, while human studies highlight neurochemical markers. Understanding these mechanisms, especially in cognitively normal older adults, requires well-designed RCTs with clear reporting of exercise characteristics.

### 1.2 Objective

[figure not shown]
The main objectives are:

1. The primary aim of the study is to investigate the effects of a 24-week resistance exercise program on executive function in cognitively normal older adults.
2. The secondary aims are (i) to examine the effects of resistance exercise on brain structural and functional markers (e.g., grey and white matter measures, functional connectivity or cerebral blood flow), brain A $\beta$  deposition, peripheral molecular markers (e.g., BDNF, IGF-1, and A $\beta$ ), and other cognitive outcomes (e.g., memory and language) and (ii) to investigate mediators and moderators of the potential exercise-derived improvements observed in executive function and brain markers.
3. The tertiary aim is to investigate the effect effects of a 24-week resistance exercise program on other outcomes including changes in muscular strength, cardiorespiratory fitness, physical function, gait parameters, mental health, quality of life, diet, body composition, blood pressure, microbiome, among others.

## 2. Study methods

## 2.1 Trail design

The AGUEDA (Active Gains in brain Using Exercise During Aging) trial is a single-centre, two-arm, single-blind RCT in which 90 cognitively normal older adults, aged 65–80 years old are randomized into a resistance exercise group ( $n = 45$ ) or a wait-list control group ( $n = 45$ ). Measurements are performed at baseline, at midpoint (12 weeks) and post intervention (24 weeks). A visual representation of the participant flow during the study can be seen in **Figure 1**. More detailed information is described in the study protocol paper (20). The study has been designed following the Standard Protocol Items for Randomized Interventional Trials (SPIRIT)(21).

**Figure 1.** Overview of the AGUEDA project

## 2.2 Randomization

Randomization (1:1) occurs on a rolling basis and only after the completion of all baseline assessment sessions by the participant to reduce the risk of bias during the assessment. We use a computerized randomization protocol (stratified by age and sex) through the REDCap Software (22) that incorporate a checklist to make sure all assessments have been completed and the data have been adequately entered into the database.

### 2.3 Sample size

We based our estimates on the AGUEDA primary outcome, i.e., change on the executive function composite score over a 24-weeks resistance exercise period. The power analysis is based on a meta-analysis which showed that the effect size of exercise intervention on executive function in older adults was 0.34 (95% Confidence interval = 0.22 to 0.47) (17) with a two-tailed alpha at 0.05 and a power of 80%. Thus, we need a sample size of 35 participants for each group to obtain such an effect size. If the maximum dropout rate is 20% plus some residual power, we then need 45 participants for each group. After all computations, we decided that the target sample size for this study will be 90 participants. More detailed information is described in the protocol paper (20)

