## 5.2 Analysis methods

The main analyses will consist of the intention-to-treat analyses for the primary and secondary outcomes using a constrained linear mixed model (cLMM). The model will include fixed effects for time (three levels or two levels, depending of the outcome) and treatment (two levels) as well as the unique participant identifier as a random effect. Model assumptions will be checked. In case we detect model violations, we will take appropriated measures by, for example, conducting data transformations. The treatment effects will be presented by estimated marginal means and standard errors for changes. The specific differences between analysis are described in the following's points divided into primary analysis, secondary and others outcomes.

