### 5.2.1 Primary analysis.

#### Effects on primary outcomes

To investigate the overall effect of the resistance exercise intervention on the change from baseline to post-intervention in the executive function composite score, cLMM approach with repeated measures over time (baseline, 12-week and 24-week outcomes) will be used using an intention-to-treat principle. This statistical linear mixed model will include both a random intercept for each participant and a group-by- time interaction as a fixed effect.

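### Section 2.3: 35 per group does not follow from an effect of 0.34, two-sided 5% and 80% power; a two-group comparison needs 137 per arm, and the planned baseline-using model needs 50 to 103 (correlations 0.8 to 0.5, score SDs)

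*SAP*

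**What the plan says.** SAP section 2.3 powers the trial on the primary outcome, the "change on the executive function composite score over a 24-weeks resistance exercise period". It takes an effect size of 0.34 (95% CI 0.22 to 0.47) from a meta-analysis, "with a two-tailed alpha at 0.05 and a power of 80" per cent, and concludes: "Thus, we need a sample size of 35 participants for each group to obtain such an effect size". It then allows for dropout: "If the maximum dropout rate is 20% plus some residual power, we then need 45 participants for each group". The target is 90 participants. For further detail it refers to the protocol paper.

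Three other parts of the SAP fix what this calculation has to match:

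- Section 2.2: "Randomization (1:1) occurs on a rolling basis".
- Section 2.4: the framework is superiority of exercise over control.
- Section 5.2.1: the target is the change from baseline to post-intervention, and the "cLMM approach with repeated measures over time (baseline, 12-week and 24-week outcomes) will be used using an intention-to-treat principle", with a random intercept and a group-by-time interaction.

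**The concern.** Section 2.3 presents 35 per group as the consequence of three stated inputs. For a between-group comparison, a standardised effect of 0.34 is modest, and 35 per arm is far fewer than it usually requires. A repeated-measures model can lower the requirement, but by how much depends on two things that section 2.3 does not give: the correlation between baseline and 24 weeks, and whether 0.34 is in SDs of the score or of the change.

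This is the SAP's only power statement, and it concerns the primary outcome. If it is wrong, readers will credit the trial with 80% power for 0.34 when it has much less. They could then take a null result as evidence against an effect of that size that the trial could easily have missed.

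**Working it through.** **Inputs.** From section 2.3: d = 0.34, two-sided alpha 0.05, power 80%, 20% dropout, 35 rising to 45 per arm. From section 2.2: 1:1 allocation. The correlation ρ between baseline and 24 weeks is not in the SAP, so I assume 0.5, 0.7 and 0.8. All power figures use the noncentral t distribution.

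**1. The plan's figure on the plan's inputs.** The normal approximation is n = 2(z₀.₉₇₅ + z₀.₈₀)²/d² = 2 × (1.960 + 0.842)²/0.34² = 2 × 7.849/0.1156 = 135.8, so 136 per arm. With the t distribution, power is 0.798 at 136 and 0.801 at 137, so 137 per arm. The stated 35 is not reproduced. Two variants do not reproduce it either: a one-sided test needs 108, and the upper confidence limit of 0.47 needs 73.

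Power for 0.34 in this comparison is 0.289 at 35 per arm, 0.296 at 36 (45 × 0.8) and 0.358 at 45. At 35 per arm, an effect of 0.68 has power 0.801.

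**2. Crediting the planned model.** With complete data, a constrained-baseline model multiplies the variance of the 24-week contrast by (1 − ρ²).

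- If 0.34 is in SDs of the score, the effective effect is 0.34/√(1 − ρ²).
- If 0.34 is in SDs of change, the difference in score SDs is 0.34√(2(1 − ρ)). Dividing by √(1 − ρ²) gives an effective effect of 0.34√(2/(1 + ρ)).

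With 2n − 3 degrees of freedom:

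| | ρ = 0.5 | ρ = 0.7 | ρ = 0.8 |
|---|---|---|---|
| Score SDs: effective effect | 0.393 | 0.476 | 0.567 |
| Score SDs: n per arm for 80% | 103 | 71 | 50 |
| Score SDs: power at 36 per arm | 38% | 51% | 66% |
| Score SDs: power at 45 per arm | 45% | 61% | 76% |
| Change SDs: effective effect | 0.393 | 0.369 | 0.358 |
| Change SDs: n per arm for 80% | 103 | 117 | 124 |
| Change SDs: power at 36 per arm | 38% | 34% | 32% |

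In score SDs, 80% power needs ρ of about 0.87 at 35 per arm, 0.86 at 36 and 0.82 at 45. In change SDs a higher correlation makes matters worse. Even at ρ = 0 the requirement is 69 per arm, so no non-negative correlation gives 35.

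**3. Partial data.** I took 36 completers plus 9 per arm seen only to week 12, in a three-visit model with equal correlations and score SDs. Power is 38.2%, 52.6% and 67.7%, which is under 2 points more than with completers alone.

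**4. Effect detectable with 80% power at 36 per arm.** Without baseline it is 0.67. In score SDs it is 0.67√(1 − ρ²) = 0.58, 0.48 and 0.40. In change SDs it is 0.67√((1 + ρ)/2) = 0.58, 0.62 and 0.64.

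**5. Where 35 might come from.** Two routes give exactly 70 in total. Both are inference, since the SAP names neither.

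- A repeated-measures interaction test with f = 0.34/2 = 0.17, two measurements and ρ = 0.5. In a 2 × 2 interaction, f = 0.17 corresponds to a between-group difference in change of 4 × 0.17 = 0.68 SD, twice the cited effect. With the matching f = 0.085, the same routine gives 274 in total, again 137 per arm.
- A paired t-test with d = 0.34, which has no control group.

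**6. Dropout.** 35/0.8 = 43.75, so 44, and 45 is consistent with 35. The fault lies in the 35 alone.

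**The case against.** The strongest reply is that section 2.3 refers to the protocol paper for detail, and that paper, which is not at hand, may state a test and a correlation. In score SDs, a correlation of about 0.87 would justify 35, and about 0.82 would give 80% power if all 45 per arm were retained. This limits what can be said about the size of the shortfall. It does not repair the SAP's own inference, which draws 35 from three inputs that do not yield it. If a correlation that high was assumed, the claim depends on it and it should stand beside the claim.

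Second, section 5.2.1 also speaks of an overall effect and models three visits. If the contrast were the average of weeks 12 and 24 with equal correlations, the need would be 69, 50 or 37 per arm at ρ = 0.5, 0.7 or 0.8, and power at 36 would be 52%, 66% or 80%. At the top of that range the gap nearly closes. But section 2.3 powers the change over 24 weeks, and section 5.2.1 targets the change from baseline to post-intervention, so this is not the stated contrast.

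Third, the unadjusted figures are not the planned analysis, and 36 per arm is a worst case because 20% is called the maximum dropout. Both points are fair, and they are why the baseline-using figures and those for 45 per arm are shown. Neither brings power to 80% within the range considered.

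Finally, type I error and the treatment-effect estimate are unaffected. That is true; what is wrong is the power the trial claims.

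**Conclusion.** The concern holds. On the stated inputs the requirement is 137 per arm, nearly four times 35, and 35 per arm gives about 29% power. That part needs no assumption beyond a 1:1 between-group comparison.

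The size of the shortfall under the planned model rests on the assumed correlations of 0.5 to 0.8, on the meaning of 0.34, and on the 24-week contrast. On those terms, power with 36 evaluable per arm is 38% to 66% in score SDs and 38% to 32% in change SDs. The design reaches 80% only in score SDs and only at a correlation of about 0.82 (all 45 per arm retained) to 0.87 (35 per arm). The power statement is wrong as written and must be corrected.

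**What to change.** Keep 90 participants and the planned analysis, and correct section 2.3 of the SAP:

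1. Remove the claim that 35 per group gives 80% power for 0.34.
2. Name the test, the assumed baseline-to-24-week correlation with its source, and whether 0.34 is in SDs of the score or of change.
3. Restate the power for 0.34 with 36 evaluable per arm: about 30% without baseline; 38%, 51% and 66% at correlations 0.5, 0.7 and 0.8 if in score SDs; 38%, 34% and 32% if in change SDs. If the assumed correlation lies outside this range, give the figure for that value.
4. State the effect detectable with 80% power at 36 per arm: about 0.67 without baseline, and 0.58, 0.48 and 0.40 at those correlations, marked as score SDs (0.58, 0.62 and 0.64 in change SDs).

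The cost is SAP wording only: the analysis, the population and the number of participants do not change. The downside is that the stated power becomes less favourable.

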## 2.4 Framework

A superiority hypothesis testing framework is used, emphasizing the evaluation of a intervention's positive impact compared to a control group. In the main analysis, we compare

resistance exercise group versus control group (no exercise) in 3-time points (Baseline, 12-week and 24-week).

### *2.5 Statistical interim analyses and stopping guidance*

No pre-specified interim analyses are performed, and therefore, a stopping guidance is not applicable.

### *2.5 Timing of the final analyses*

The main final analyses will be performed after the finalization of the data processing of the primary outcome.

### *2.6 Timing of outcome assessment*

The primary outcome is assessed at baseline, midpoint (12 weeks) and post intervention (24 weeks). In addition, there are other secondary outcomes only assessed at baseline and post intervention. The time frame of each outcome is explained in section *5.1 Outcome definitions*.

## **3. Statistical principles**

### *3.1 Confidence and P values*

All statistical tests are two-tailed. *P* for significance will be set at 0.05 and 95% confidence intervals will be estimated.

### *3.2 Adherence and protocol deviations*

Adherence to the exercise program is measured by session attendance which is the proportion of sessions attended out of the total offered sessions.

All protocol deviations made to the protocol (e.g. change in pre-defined inclusion/exclusion criteria, baseline and post assessments, data cleaning/processing) will be reported and described in the analysis.

### *3.3 Analysis populations*

Three analytic datasets will be defined for the statistical analyses:

1. Intention-to-treat: This dataset will be used for our primary analyses and includes all randomly assigned study participants. With this approach, all randomized participants are included in the main analysis.
2. Per protocol: This dataset will be used for our secondary analyses and includes all participants who followed the attendance rate. As such, as the 100% of the session corresponding to a total of 72 sessions (3 session per week for 24 weeks), 80% attendance is required for be included per protocol analyses, corresponding to  $\geq 57$  exercise sessions.

## **4. Trial population**

### *4.1 Recruitment*

We began recruitment of community-dwelling older adults in Granada (Spain) city and surrounding areas in March 2021. Strategies to achieve the targeted sample size mainly include mass mailings and social media advertisements, word of mouth, with augmentation of the recruitment strategy by using advertisements in newspapers (TV, radio, and internet).

Information necessary for the CONSORT flow diagram is collected. For the enrollment phase, we note the number of participants that were assessed for eligibility by the research team, the number of excluded participants (plus reason for exclusion), and the number of randomized participants. For the allocation, the number of participants allocated to the intervention and control group is noted. For follow-up, the number of participants lost to follow-up (12-week and 24-week) and the number who discontinued the intervention (plus reasons) are counted. Finally, the number of participants included in the analyses using the intention-to-treat and per-protocol databases is described, along with the reasons for exclusion.

#### *4.2 Initial phone screening*

Following recruitment strategies and after the participant's first contact for general information, a phone screening is performed with those individuals who are potentially interested in participating. Then, participants meeting the phone criteria are invited to the on-site screening, and those who met the on-site criteria are enrolled in the study.

#### *4.3 Eligibility*

Inclusion and exclusion criteria is defined as follows: (i) older adults between 65 - 80 years, (ii) physically inactive (i.e., defined as not participating in any resistance exercise program in the last 6 months or accumulating less than 600 METs-Min/week by the International Physical Activity Questionnaire (IPAQ) (23), (iii) classified as cognitively normal according to the Spanish version of the modified Telephone Interview of Cognitive Status (STICS-m) ( $\geq 26$  points) (24), Mini-Mental State Examination (MMSE) ( $\square 25/30$ ) (25) and Montreal Cognitive Assessment (MoCA) ( $<71$  years,  $\square 24/30$ ,  $71-75 \square 22/30$ ,  $>75, 21/30$ ) (26); and (iv) without significant depressive symptoms at baseline according to the Geriatric Depression Scale (GDS) ( $\square 15$ ) (27). Detailed information about the study design is available elsewhere(20).

#### *4.4 Withdrawal/follow-up*

The number, timing, and reasons (e.g. adverse events, withdraw consent, lost to follow-up) for withdrawal is noted and described.

#### *4.5 Baseline patient characteristics*

A baseline data table is created to describe the characteristics of the study population. The main characteristics include age, sex, education, body mass index and the outcomes variables. The characteristics of the total study population and each study arm is summarized using mean (SD) or median (interquartile range) for normally and not normally distributed continuous variables, respectively, and as number (percentage) for categorical variables.

## 5. Analysis

### 5.1 Outcome definitions

The primary outcome is assessed at baseline (before randomization), at mid-point (12-week) and after the intervention (24-week) while some of secondary outcomes are assessed only at baseline and post intervention (24-week, Table 1).

Table 1. Time frame and specific outcomes of cognitive tests.

Executive function test	Baseline	12-week	24-week	Specific outcome
Trail making test A and B	x	x	x	Interference score
Digit symbol substitution test	x	x	x	Total number of correctly paired symbols
Dimensional card sort task	x		x	Inverse efficiency score
Spatial working memory	x	x	x	Inverse efficiency score
Picture sequence	x		x	Theta score
List sort working memory	x		x	Raw score corrects trials
Flanker	x		x	Incongruent trials inverse efficiency score
Stroop task	x	x	x	Interference score
Task-switching	x	x	x	Global Cost
Other cognitive test	Baseline	12-week	24-week	Specific outcome
Rey auditory verbal learning test	x		x	Total recorded words
Rey-Osterrieth complex figure	x		x	Correct drawn elements
Boston Naming Test	x		x	Correct responses
Wechsler adult intelligence scale IV				
T Similarities				
T Vocabulary	x		x	
T Information				
T Block design				
T Matrix reasoning				
T Visual puzzles				
Verbal and semantic fluency test	x	x	x	Correct responses

### Primary outcome

The primary outcome of the AGUEDA project is the change on the executive function Executive function composite score (Z-score) which will be created by performed confirmatory factor analyses (CFA). CFA will include the executive function variables and the final model will be choose based on the fit of the model considering  $\chi^2$  p-value  $\geq .05$ , Bentler Comparative Fit Index (CFI)  $> .95$ , Steiger-Lind Root Mean Squared Error of Approximation (RMSEA)  $< .08$  as a good model fit (28).

The executive function tests included to perform the CFA will be:

- ⠁ Trail Making Test (29). The difference in the time between trail A and trail B (TMT B-A) is calculated and the inverse variable will be used.
- ⠁ Design symbol substitution test (30). The variable to use is the total numbers of correct symbols score.
- ⠁ Dimensional Change Card Sort Test (31). The variable used will be the inverse efficiency score of color trials (Reaction time/ Accuracy).
- ⠁ Spatial working memory (13). Performance is measured based on accuracy, response times, and errors. The variable used will be the inverse efficiency score (Reaction time/ Accuracy) of all trials (2,3,4 items).

- ि Picture Sequence Memory Test (31). The participant's score is derived from the cumulative number of adjacent pairs of pictures remembered correctly over three learning trials, the theta score.
- ि List Sort Memory Test (31). Scores are calculated by summing the total number of correct responses across both lists.
- ि Flanker (31). The interference from reporting the direction of the middle arrow and not the external arrows will be calculated by subtracting the average incongruent accuracy from that of the congruent trials.
- ि Stroop test. The interference score from the incongruent trials will be calculated.
- ि Task Switching (32). The difference in mean reaction time for the mixed block of trials, including both the repeat and switch trials, is calculated as a global cost score.

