#### *Effects on other outcomes*

To investigate the effect of the resistance exercise intervention on other outcomes (i.e., biological biomarkers, physical function, muscular strength, physical activity, Anthropometric, body composition and blood pressure and Psychosocial, mental health and other questionnaires) the same analyses as the primary analysis using an intention-to-treat principle and cLMM analysis will be performed.

Furthermore, analyses per protocol will be followed of the executive function variables (ie., Executive function score, Trail making test, Digit symbol substitution score, Dimensional change card sort test and Spatial working memory).

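### The primary composite is chosen by model fit, but the fit cut-offs do not identify one model, and the SAP states no dataset, masking, fixed scoring or fallback for that choice

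*SAP*

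**What the plan says.** Section 5.1 (Primary outcome) makes the primary outcome the change in a Z-score composite obtained by CFA. On how the model is settled it says: "CFA will include the executive function variables and the final model will be choose based on the fit of the model", with chi-square p of at least .05, CFI above .95 and RMSEA below .08 counting as good fit.

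The inputs are introduced by "The executive function tests included to perform the CFA will be", followed by nine tests, each with a scoring variable. Only the Trail Making variable is said to be inverted.

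On timing, section 5.1 says: "The primary outcome is assessed at baseline (before randomization), at mid-point (12-week) and after the intervention (24-week"). Section 5.2.1 models the composite at all three visits. Table 1 marks five of the nine tests at 12 weeks (Trail Making, Digit Symbol, spatial working memory, Stroop, task switching). It marks no 12-week measurement for card sort, picture sequence, list sort or Flanker.

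Section 2.1 says the trial "is a single-centre, two-arm, single-blind RCT", without linking the blinding to the CFA. Section 2.5 on timing says: "The main final analyses will be performed after the finalization of the data processing of the primary outcome".

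**The concern.** A threshold tells the analyst whether a model is acceptable. It does not say which of several acceptable models to use. The SAP gives no number of factors, no list or order of candidate models and no tie-break. It does not say whether a test may be dropped or residual correlations added. It does not say which visit supplies the data, whether loadings are held fixed over visits, whether the person choosing is masked, or what happens if nothing fits.

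Two analysts following the text could therefore test different primary endpoints. The single 5% test is secure if the composite is fixed without sight of results by arm. The SAP does not require that order of work.

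The text also forces at least one unstated decision: the nine-test composite cannot be computed at 12 weeks from the tests in Table 1. A smaller conflict adds to this. The Flanker variable is an inverse efficiency score on incongruent trials in Table 1, but a difference in accuracy between congruent and incongruent trials under Primary outcome.

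**Working it through.** The SAP gives no figure for this step, so there is none to reproduce.

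**Inputs from the SAP:** nine tests; the three cut-offs; 90 participants, 45 per arm; two-sided alpha 0.05.

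**Inputs assumed, because the SAP has none:** loadings and factor correlations as in the table; retest correlation 0.7; complete data.

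**1. Size of the choice if tests may be dropped.** Subsets of at least four of nine tests: C(9,4) + C(9,5) + C(9,6) + C(9,7) + C(9,8) + C(9,9) = 126 + 126 + 84 + 36 + 9 + 1 = 382. The 84 three-test subsets are left out because a one-factor model on three tests has zero degrees of freedom, so its fit cannot be tested.

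**2. How many pass.** There were 250 simulated trials per row, n = 90, with no treatment effect. A one-factor maximum-likelihood model was fitted to baseline data for every subset and all three cut-offs were applied. Number passing = share × 382, for example 0.217 × 382 ≈ 83 and 0.826 × 382 ≈ 316.

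| Assumed structure | Mean share of subsets passing | About | Nine-test one-factor model passes |
|---|---|---|---|
| One factor, loadings 0.3–0.6 | 74% | 283 | 68% |
| One factor, loadings 0.4–0.8 | 83% | 316 | 90% |
| Three factors correlated 0.7, loadings 0.6 | 57% | 219 | 32% |
| Two factors correlated 0.6, loadings 0.6 | 43% | 165 | 14% |
| Three factors correlated 0.5, loadings 0.7 | 23% | 89 | 0% |
| Two factors correlated 0.4, loadings 0.7 | 22% | 83 | 0% |

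Many subsets pass in every row. Whether most do depends on the structure. With two or three factors the nine-test one-factor model fails in 68% to 100% of trials, so a fallback is a realistic need.

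**3. What free choice could do to the error rate.** In the same trials, 24-week factor scores were compared between arms with baseline adjustment.
- Nine-test score fixed in advance: type I error 3% to 7%, consistent with 5% (Monte Carlo standard error about 1.4 points).
- Smallest p-value among all subsets that pass: 23% to 41% (standard error about 3 points near 40%). In the direction of benefit: 12% to 22%, against a nominal 2.5%.

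A second simulation used 2,000 null trials, 35 per arm, pairwise correlations 0.2 to 0.4, equal-weight means and no fit filter. A fixed composite gave 5.0% to 5.5%. The smallest p-value among 5, 10 or 382 subsets gave 10.4% to 13.4%, 13.2% to 18.1% and 26.6% to 40.6%.

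**4. The narrower reading: all nine tests stay.** Scorings considered: the basic one-factor model, the same model with any one residual correlation (C(9,2) = 36), and the equal-weight mean, so 1 + 36 + 1 = 38. Settings: n = 90, pairwise correlations 0.2 to 0.4, retest 0.7, 600 null trials per setting. These scores correlate with the basic model at a median above 0.99. The smallest p-value among all 38 gives 5.7% to 6.3%, against 4.2% to 4.7% for one fixed score (standard error about 0.9 points). Multi-factor models were not tested here.

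**The case against.** The strongest reply is that much is already fixed: nine named tests, a variable for each and three numerical cut-offs. The SAP never says that tests may be dropped, and a fair reading keeps all nine and lets fit decide only the structure. Step 4 shows that small changes to a nine-test, one-factor model then hardly matter. This stands, and it means that the larger error rates depend on a permission the SAP does not give. It does not close the gap. If the nine-test one-factor model fails, something must change, and the SAP does not say what. A two- or three-factor model does not by itself yield one composite.

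It is also fair that fit is judged without using treatment arm, that the timing statement in section 2.5 suggests the composite is built before the main comparison, and that section 3.2 promises to report deviations in data processing. But the timing statement neither masks nor locks the choice, and an open rule leaves little to deviate from.

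A reader might infer from section 5.2.2 that the composite has been reduced to four tests, since the per-protocol analyses name "Executive function score, Trail making test, Digit symbol substitution score, Dimensional change card sort test and Spatial working memory" and the moderator list repeats those four. The text does not support this. Both places list component tests alongside the composite for separate analyses, which is legitimate, and neither redefines the primary outcome.

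**Conclusion.** The point stands in this form: the SAP lets fit on trial data decide the primary composite, the cut-offs do not identify one model, and dataset, masking, scoring over visits and fallback are not stated. This matters because it concerns the trial's single primary endpoint.

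Two stronger conclusions are tempting but not supported. One is that most test subsets would pass: the share runs from 22% to 83% according to correlations that the SAP does not give. The other is that the trial's type I error is 10% to 41%. Every figure in that range assumes selection by p-value among test subsets, whereas the plan selects on fit. They also rest on assumed correlations and a baseline-adjusted 24-week comparison in place of the planned constrained mixed model. They are worst-case illustrations. If the choice is made on baseline data or under masking, the 5% level is not at risk from this source. Nothing in the SAP shows that a selective choice was made.

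**What to change.** Amend section 5.1 (Primary outcome) as follows, to be carried out before any comparison by arm:

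- **Model.** Name one starting model: one factor, named tests, every variable signed so that higher is better. Fit it once, on baseline data only, by someone masked to allocation. Give one ordered rule for modifying it.
- **Scoring.** Freeze the loadings and the baseline mean and SD, and apply them unchanged at later visits.
- **Fallback.** If no model meets the cut-offs, use the equal-weight mean of the baseline-standardised scores of the named tests. The signs matter here, since such a mean cannot correct a reversed variable as a loading can.
- **12 weeks.** State one of two options. Either build the composite only from the five tests measured at all three visits, or keep the full composite and analyse it at baseline and 24 weeks only. The second option also changes sections 2.4, 2.6 and 5.2.1. The first leaves C(5,4) + C(5,5) = 6 subsets of at least four tests instead of 382.
- **Flanker.** Use one variable in both Table 1 and the Primary outcome list.

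The component tests in section 5.2.2 need not match the composite.

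The cost is SAP wording and one masked baseline analysis, with no new data. The frozen model may fit slightly less well at follow-up, and a five-test composite covers fewer tests.
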